#### 6.1.4 Medical History

Medical History will be coded using the Medical Dictionary for Regulatory Activities (MedDRA) Version 26.0 and will be listed by System Organ Class and Preferred Term.

A listing of medical history will be provided.

#### 6.1.5 Prior and Concomitant Medication

The incidence of medication use will be summarized by WHO Drug Dictionary (WHODD) B3 Global March 2023 anatomic therapeutic chemical (ATC) Level 2 classification (i.e. therapeutic main group) and preferred name. A participant will be counted only once at each level of reporting. Prior medications are those which have been identified to have been discontinued prior to the treatment start date (e.g., taken exclusively during the pre-therapy period). Concomitant medications are those which have been identified to have been taken at any point during the on-therapy or post-therapy periods. Prior and concomitant medication use will be summarized separately.

All prior and concomitant medication data will be listed including the verbatim and preferred drug name and ATC Level 2. If anticancer medications have been recorded as taken during study, these will be identified via medical review and flagged in data listings.

##### 6.1.5.1 PJP Prophylaxis Antibiotic Treatment

The incidence of PJP Prophylaxis Antibiotic Treatment use will be summarized. A participant will be counted only once for any use.

All PJP Prophylaxis Antibiotic Treatment data will be listed.

#### 6.1.6 Prior and Concomitant Procedures

Number and percentages of prior and concomitant procedures will be summarized by indication, procedure, location, and laterality. Prior procedures are those which have been identified to have

been discontinued prior to the procedures start date (e.g., taken exclusively during the pre-therapy period). Concomitant procedures are those which have been identified to have been taken at any point during the on-therapy or post-therapy periods. Prior and concomitant procedures will be presented in data listings.

### 6.1.7 Study Drug Exposure and Compliance

For both Ad/PNP and F-araAMP (separately), completion of a given cycle is defined as follows:

- Completed cycle is defined as all 3 administrations performed.
- Partial cycle is defined as < 3 administrations performed.

Note that, based on the data collection in the eCRF, an administration is either performed or not performed; there is no consideration of partially vs. fully performing an administration. In contrast, a partial Ad/PNP injection or a partial F-araAMP infusion are considered below.

For Ad/PNP, an administration is defined farther below. For F-araAMP, an administration is defined as a full infusion or a partial infusion.

Exposure to Ad/PNP will be summarized using the following measures:

- Total Number of Cycles Completed.
- Total Number of Cycles Received. Defined as the total number of completed or partial cycles.
- Number of administrations performed
- Number of administrations not performed
- Number of administrations delayed
- Number of injections administered (fully or partially)
- Number of injections fully administered
- Number of injections partially administered
- Number of injections not administered
- Treatment Duration (days): Last dose date - First dose date + 1

For the Ad/PNP exposure endpoints listed above, a single Ad/PNP administration is defined without regard to the number of injections or the number of tumors treated, while the number of injections is defined considering the number of tumors treated. For example, a participant might have:

- 3 administrations during any given cycle, comprised of
  - 1 tumor treated at each administration, yielding a total of 3 injections.
- or,
- 3 administrations during any given cycle, comprised of
  - 2 tumors treated at each administration, yielding a total of 6 injections.

F-araAMP exposure will also be summarized using mg/m^2.

- Total Number of Cycles Completed.
- Total Number of Cycles Received. Defined as the total number of completed or partial cycles.

- Total Cumulative Dose Received. Defined as total mg/m^2 received from first dose date up to and including last dose date.
- Number of infusions administered (fully or partially)
- Number of infusions which were temporarily interrupted or had flow rate modified.
- Number of infusions fully administered
- Number of infusions partially administered
- Number of infusions not administered
- Number of infusions delayed
- Dose Intensity (mg/m^2/Cycle). Defined as [total cumulative dose (mg/m^2)] / [number of Cycles Received].
- Treatment Duration (days): Last dose date - First dose date + 1

No assessment of study drug compliance will be performed for this study.

## 6.2 Efficacy

Efficacy analyses will be conducted on the Efficacy Evaluable Population (refer to section 4).

In addition to the tabular summaries detailed below, efficacy data will be provided in by-participant data listings.

### 6.2.1 Primary Efficacy Endpoint(s) and Analyses

There is no primary efficacy endpoint, and therefore no primary efficacy analysis, as the primary endpoint for this study is safety. However, an efficacy endpoint of primary focus is defined in section 6.2.2.

### 6.2.2 Secondary Efficacy Endpoints and Analyses

Secondary efficacy endpoints involving response, including progression, will be assessed 2 distinct ways:

- For injected tumors (per the criteria specified in protocol section 9.3.4), and
- Overall as determined per RECIST v1.1 (<http://www.ctep.info.nih.gov>).

Efficacy responses assessments for injected tumors should be performed using the (RECIST-like) assessment according to the criteria established in section 9.3.4 (Tumor Response) of the protocol (CR, PR, PD, SD). Per the protocol, this response for injected tumors is the primary focus for response, with the efficacy endpoint of primary focus being ORR for injected tumors.

Overall efficacy response assessments should be performed per RECIST 1.1 for target and non-target tumors without consideration for which tumors were treated with the study agent. Per the protocol, this overall response per RECIST 1.1 is not the primary focus for response. Total tumor burden is also being evaluated because there is a possibility of immune-mediated anti-tumor benefit.

RECIST and protocol established response evaluation criteria should be performed/evaluated in combination with CT scan/MRI at the timepoints specified in the protocol (Visit 7 of the first,

second (if PD after first cycle), third, and last cycle. Participants with CR, PR, or SD in the injected tumor at Day 14 of the fifth or last cycle will have imaging on Day 56).

To emphasize:

- Injected tumors will not be assessed per RECIST v1.1 but solely per the criteria (from protocol section 9.3.4) which are specified below.
- Many of the endpoints differ for injected tumors vs. overall as determined per RECIST v.1.1 due to differences in their underlying component definitions of CR, PR, and PD.
- All efficacy endpoints are secondary.

### **Injected Tumor Response Criteria Details**

The following criteria will be used to define response in injected tumors:

- Complete Response (CR): Disappearance of the injected tumor(s).
- Partial Response (PR): At least a 30% decrease in the longest diameter (LD) of the injected tumor(s), taking as reference the smallest LD.
- Progression (PD): At least a 20% increase in the LD of the injected lesion(s), taking as reference the smallest LD recorded on study (this includes the baseline LD if that is the smallest on study). Note: appearance of one or more new lesions will be considered progression in assessing overall tumor response.
- Stable disease (SD): Neither sufficient shrinkage to qualify for PR nor sufficient increase to qualify for PD taking as reference the smallest LD while on study.

Regarding injected tumors, only tumors identified as target per RECIST 1.1 at the initial study visit should be treated with the study agent (AdPNP). It is possible, based on the size(s) and location(s) of the target tumor(s), that not all target tumors will be treated with the study agent. At each administration, investigators should treat only the same tumor(s) based on those target tumors treated at the initial treatment visit. No other target tumors should be treated with the study agent at any subsequent visit. Non-target tumors should not be treated with the study agent. Response for injected lesions is assessed by the investigator and recorded in the eCRF.

Regarding non-injected tumors, the protocol does not define response assessment criteria for these tumors. Therefore, efficacy response for non-injected tumors will be taken into consideration only as an input to the RECIST 1.1 response assessment. No formal criteria-based response assessment will be performed or analyzed for non-target tumors alone. Any observable effect on non-injected tumors may be recorded by investigators in the study database.

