3.1 Inclusion Criteria

1. Provided Informed Consent
2. Age \geq 18 years
3. Patients with histologically or cytologically confirmed diagnosis recurrent cancer of the head and neck region for whom there is no curative treatment option. For the purposes of trial eligibility, cancers of the head and neck region shall include, in addition to HNSCC, cutaneous squamous cell primary sites and squamous cell carcinoma of unknown primary presenting with neck lymph nodal disease, as well as nasopharyngeal carcinoma, and salivary gland tumors.
4. All standard or approved treatment options that would provide substantive palliation must have failed, been exhausted, or patient not eligible for them (for example neuropathy, nephropathy, or hearing loss precluding the use of cisplatin)
5. Tumor mass (primary tumor and/or lymphadenopathy) measurable by RECIST 1.1 and technically suitable for intratumoral injections (otolaryngologist will determine feasibility). Patients with nodal disease (or metastatic disease) that is needle accessible are eligible. Patients with additional tumors (including distant metastatic disease) beyond the intratumoral injection accessible tumor(s) that are not accessible for intratumoral injection are eligible ONLY if the patient has no other treatment option for the metastatic disease and treatment of local disease may provide the patient some benefit or palliation.
6. Eastern Cooperative Oncology Group (ECOG) performance status of \leq 2.
7. In the judgment of the investigator, the patient has recovered sufficiently from any previous significant therapy side effects or toxicities prior to Ad/PNP administration.
8. Absolute neutrophil count [ANC] \geq 1,500 cells/ μ l; hemoglobin \geq 9 g/dl, platelets \geq 100,000/ μ l.
9. Serum creatinine \leq 1.5 mg/dl, or calculated creatinine clearance \geq 60 ml/min.

10. Bilirubin \leq upper limit normal [ULN], alanine aminotransferase [ALT] $\leq 1.5 \times$ ULN and/or aspartate aminotransferase [AST] $\leq 1.5 \times$ ULN, alkaline phosphatase $\leq 2.5 \times$ ULN.
11. Prothrombin time (PT)/international normalized ratio (INR) $\leq 1.5 \times$ ULN.
12. Activated partial thromboplastin (aPTT) time $\leq 1.5 \times$ ULN.
13. Female patients must have a negative urine or serum pregnancy at screening (pregnancy test is not required for patients with bilateral oophorectomy and/or hysterectomy or for those patients who are > 1 year postmenopausal).

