9.3.4 Tumor Response

For this study, response will focus on the injected tumor(s) and be based on criteria according to those in RECIST v1.1.[6] In addition, overall tumor response will be assessed according to RECIST 1.1 criteria.

The following criteria will be used to define response in injected tumor(s):

- Complete Response (CR): Disappearance of the injected tumor(s).
- Partial Response (PR): At least a 30% decrease in the longest diameter (LD) of the injected tumor(s), taking as reference the smallest LD.
- Progression (PD): At least a 20% increase in the LD of the injected lesion(s), taking as reference the smallest LD recorded on study (this includes the baseline LD if that is the smallest on study). Note: appearance of one or more new lesions will be considered progression in assessing overall tumor response.
- Stable disease (SD): Neither sufficient shrinkage to qualify for PR nor sufficient increase to qualify for PD taking as reference the smallest LD while on study.

Target tumors accessible for needle injection on physical examination will be injected. Size of the injected tumor masses will be measured with ruler or calipers, as possible, and it is preferable if the same practitioner measures using the same technique at each visit.

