10.3.3 Measurement Methods

Primary outcome measurement methods will include clinical evaluation (physical examination, medical history, performance status, vital signs, evaluation of tumor site for evidence of tissue injury) by investigators conducting the study (or their designees). Laboratory and additional parameters (EKG, CXR, blood chemistry, hematology, CD4/CD8 T-cell counts, urine analysis, PT/PTT, etc.) will be measured according to standard hospital/clinic procedures, and as detailed in Section 7 of this document.

Secondary outcome measurement methods are defined in Sections 9.3.4 and 9.3.5 and will be performed according to RECIST 1.1.

Special Studies include

Blood samples for adenovirus, urine for adenovirus, F-Ade plasma level, blood sample for antibody against adenovirus, tumor biopsy for studies of PNP activity, histochemistry, growth fraction, and adenoviral distribution. Specific studies are described in Section 8.

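### The injected-tumor criteria contain no lymph-node rule, so an injected node cleared of tumor but still visible has no defined route to CR and scores PR or SD by its longest diameter

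*SAP*

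**What the plan says.** Nodes can be the injected lesion. Protocol 3.1, criterion 5, counts lymphadenopathy as a qualifying tumor mass and adds: "Patients with nodal disease (or metastatic disease) that is needle accessible are eligible". Criterion 3 also admits squamous cell carcinoma of unknown primary that presents in neck nodes.

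One set of criteria covers every injected lesion. In SAP 6.2.2 (Injected Tumor Response Criteria Details), which repeats protocol 9.3.4:
- CR: "Complete Response (CR): Disappearance of the injected tumor(s".
- PR: "At least a 30% decrease in the longest diameter (LD) of the injected tumor(s), taking as reference the smallest LD".
- SD: "Neither sufficient shrinkage to qualify for PR nor sufficient increase to qualify for PD taking as reference the smallest LD while on study".
- PD: an increase of at least 20% in LD.

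Neither document adds a nodal measure, a normal-size threshold or any other exception.

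On RECIST the two documents differ. The SAP states: "Injected tumors will not be assessed per RECIST v1.1 but solely per the criteria (from protocol section 9.3.4) which are specified below". Protocol 9.3.4 says that "response will focus on the injected tumor(s) and be based on criteria according to those in RECIST v1.1", and protocol 10.3.3 says: "Secondary outcome measurement methods are defined in Sections 9.3.4 and 9.3.5 and will be performed according to RECIST 1.1". Protocol 10.3.5 also bases response on RECIST v1.1. SAP 1.1 states that no analysis specified in the protocol was changed.

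The investigator assesses response for injected lesions (SAP 6.2.2). Three sites are named (SAP 3.1, protocol 12.1).

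**The concern.** A lymph node is a normal structure. If treatment clears the tumor in it, a node with a non-zero diameter can remain. A rule that asks for disappearance suits a mass that can vanish. It does not say how to grade a node that is free of tumor and still visible on the scan or to the calipers. Because the SAP confines grading to these criteria, an investigator who follows it cannot look to RECIST 1.1 for the missing rule. An investigator who follows the protocol might.

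Two things are at stake. BOR for injected tumors is reported by category, so the split between CR, PR and SD would depend partly on how each site reads one word. And ORR for injected tumors is the efficacy analysis of primary focus (SAP 6.2.2.1). In a population of about 10, one participant moved from response to SD is visible in the result.

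**Working it through.** **1. The passages side by side.**

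| Question | SAP 6.2.2 | Protocol |
|---|---|---|
| May a node be injected? | Yes, if it is a RECIST 1.1 target lesion | Yes (3.1, criterion 5) |
| CR for an injected lesion | Disappearance | Disappearance (9.3.4) |
| Measure for PR, SD, PD | LD | LD (9.3.4) |
| Does RECIST 1.1 apply to injected-tumor response? | No | Tied to it (9.3.4, 10.3.3, 10.3.5) |
| Nodal rule | None | None |

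The case of a cleared but visible node is therefore not provided for. On the literal text it fails CR and falls to the LD rule.

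**2. The plan's own figure.** Inputs from SAP 3.3 and protocol 12.1: n = 10, reject at 3 or more responses, null ORR 10%, alternative 40%.
- Alpha = 1 − (0.9^10 + 10 × 0.1 × 0.9^9 + 45 × 0.1² × 0.9^8) = 1 − (0.3487 + 0.3874 + 0.1937) = 0.0702.
- Power = 1 − (0.6^10 + 10 × 0.4 × 0.6^9 + 45 × 0.4² × 0.6^8) = 1 − (0.0060 + 0.0403 + 0.1209) = 0.8327.

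These reproduce the stated 7% and 83%.

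**3. Where PR ends and SD begins.** Consider a participant with one injected node. I take baseline as the reference, which is the smallest LD available at the first post-baseline assessment. How the reference should work at later assessments is a separate question. PR needs residual LD ≤ 0.70 × baseline LD, so baseline LD must be at least residual ÷ 0.70. The residual sizes below are assumptions; the documents give none.

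| Assumed residual LD (mm) | Smallest baseline LD that scores PR (mm) |
|---|---|
| 8 | 8 ÷ 0.70 = 11.4 |
| 10 | 10 ÷ 0.70 = 14.3 |
| 12 | 12 ÷ 0.70 = 17.1 |
| 15 | 15 ÷ 0.70 = 21.4 |

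Examples: 15 to 10 mm is −33.3%, PR; 15 to 12 mm is −20.0%, SD; 20 to 14 mm is −30.0%, PR; 20 to 15 mm is −25.0%, SD. A cleared node scores SD only if more than 70% of its reference LD remains.

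**4. Effect on ORR.** ORR counts CR and PR alike.
- Node scored PR instead of CR: ORR changes by 0.
- Node scored SD, with no response at any other assessment: ORR falls by 1 ÷ 10 = 10 percentage points.

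**5. Sensitivity of the 3-of-10 rule.** Let f be the share of true responders who score SD for this reason. The observed rate is then 0.40 × (1 − f), and the chance of 3 or more responses in 10 is:

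| f (assumed) | Rate | Probability of 3 or more |
|---|---|---|
| 0 | 0.40 | 0.8327 |
| 0.10 | 0.36 | 0.7595 |
| 0.20 | 0.32 | 0.6687 |
| 0.25 | 0.30 | 0.6172 |
| 0.50 | 0.20 | 0.3222 |

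The documents give no basis for choosing f, so this shows sensitivity only. SAP 3.3 also does not say whether its rule uses injected-tumor or overall ORR.

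**The case against.** The best reply is that the CR criterion speaks of the tumor and not of the node. When the tumor within a node has gone, an investigator may fairly say it has disappeared and score CR. This stands as far as it goes: a reader might infer that a nodal participant can never reach CR, and the text does not force that. But nothing says when a residual node counts as free of tumor, so the latitude is itself a source of inconsistent grading.

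A second reply is that a reader might infer that a small cleared node can score only SD. That is wrong: SD follows only when more than 70% of the reference LD remains. The residual sizes used above are assumed, and nothing in the documents shows how small an injected node may be.

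Third, CR scored as PR leaves ORR and the 3-of-10 rule untouched, and where other lesions are injected too, the grade depends on them as well. Both points stand and limit the effect.

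Fourth, the SAP openly says that the injected-tumor and overall definitions differ, labels the former RECIST-like, and reports the two separately. That is fair notice of a difference. It does not supply a rule for nodes, and it does not settle the conflict with the protocol's references to RECIST 1.1.

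Finally, one might argue that the same node would be CR in the overall table. The documents do not reproduce the RECIST 1.1 nodal rule, so they do not support that claim and it is not made here.

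**Conclusion.** The concern holds as a gap in the response definition. The criteria apply disappearance and LD to every injected lesion although nodes may be injected, and the SAP closes off RECIST 1.1 where the protocol points to it. A cleared node that stays visible has no defined route to CR. On the literal reading it is PR at a fall in LD of 30% or more and SD otherwise, and three sites may grade it differently.

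The direct effect is on the BOR categories. Injected-tumor ORR changes only through nodes scored SD, by 10 points per affected participant with 10 evaluable. The total effect cannot be computed, because the number and size of injected nodes are not given. The boundary figures assume a single injected node, baseline as reference and residual LDs of 8 to 15 mm; the power figures assume f. The documents do not support the stronger conclusions that CR is impossible for all nodal participants or that ORR is lowered in all of them.

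**What to change.** Make three changes for response scoring, before database lock:

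1. In SAP 6.2.2 and protocol 9.3.4, state that an injected lymph node is measured and graded by the RECIST v1.1 lymph-node rules already applied to that node for overall response. Write out the measure and the CR condition, since neither document does so now.
2. Keep disappearance as the CR requirement for non-nodal lesions.
3. In SAP 6.2.2, except nodes from the statement that injected tumors are graded solely by the protocol 9.3.4 criteria. This also brings the SAP closer to protocol 10.3.3 and 10.3.5.

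No new scans are needed: only RECIST 1.1 target lesions should be injected (SAP 6.2.2), and they are already assessed under RECIST 1.1 for overall response. The statistical downside is that two lesion types would be graded by slightly different rules.

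The change is not purely one of wording. Protocol 4.2 makes treatment depend on CR and on whether tumor is present for injection. Those provisions must be reconciled with the response definition; no clinical rule is proposed here.

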4.2 Administration of Ad/PNP-F-araAMP per Cycle

With each cycle, subjects will receive 3 intratumoral administrations of 2.0×10^{11} VP Ad/PNP over 2 days followed by 3 daily infusions of 25 mg/m^2 F-araAMP in the outpatient clinic or in-hospital at the discretion of the investigator. The physician or a designee trained to do the injections by the Principal Investigator (PI) will administer intratumoral Ad/PNP during each cycle. The outpatient unit is staffed with medical personnel to treat emergency and non-emergency medical events.

Ad/PNP will be given via direct intratumoral injection three times over 2 days. If needed, the investigator may utilize radiologic guidance (e.g., ultrasound) to assist in the injection of Ad/PNP. Two intratumoral administrations will be given on Day 1 and one intratumoral administration on Day 2. The first administration will occur on the morning of Day 1 and the subject monitored closely for 1 hour for acute injection-related events. Approximately 3-6 hours after the first administration, the subject will receive the second intratumoral administration on Day 1. The third intratumoral administration will be given on the morning of Day 2.

Vials of Ad/PNP will be thawed and prepared for injection by the investigational pharmacy according to the Preparation of Investigational Product Instructions. In the Phase 1 study, Ad/PNP was administered intratumorally in a 0.5 ml volume ($\sim 2 \times 10^{11}$ VP/ml or $\sim 2 \times 10^{12}$ VP/ml); both dose levels showed activity and were well tolerated. In the Phase 1/2 study, 2×10^{11} VP will be administered in volumes up to 5 ml (4×10^{10} VP/ml) so that vector can be dispersed more effectively throughout needle-assessable tumor tissue.

The volume of vector injected into each tumor will be according to tumor volume. All measurable tumors that are accessible for intratumoral injection will be identified and treated for each enrolled subject

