## 5.2 General Definitions

Variable	Definition
Study Day	

• Study Day = date of interest - reference date + 1, when the date of interest <math>\geq</math> reference date;

• otherwise, Study Day = date of interest - reference date.

 
Note: if either day is missing, reference date calculations will not be performed. Should imputation be performed, then Study day may be computed, where appropriate.

Baseline	Defined as the last non-missing value collected prior to receiving the first intratumoral injection (based on date and time of administration as applicable).
Post-baseline	Defined as values collected after receipt of first intratumoral injection (based on date and time of administration as applicable)
Change from Baseline	Defined as: Post-baseline value - Baseline value

Percent Change from Baseline	Defined as: (Post-baseline value - Baseline value)/Baseline value x 100.  Note: To calculate percent change from baseline, the baseline value cannot be equal to zero.
Most Extreme Change	The maximum most extreme change will be based on the maximum post-baseline value; the minimum most extreme change will be based on the smallest post-baseline value. For laboratory data assessed with CTCAE grading, data from scheduled or unscheduled visits will be utilized.
Maximum Reduction from Baseline	The maximum reduction from baseline will be based on the minimum post-baseline value collected and calculated per the change from baseline formula above. For tumor measurements, post-baseline values will be considered until an overall response of PD; measurements collected after start of new cancer therapies will not be included.
Maximum Percent Reduction	Defined as the percent change that is associated with the minimum most extreme change (i.e., the largest decrease from baseline). For tumor measurements, the maximum percent reduction will be the percent change from baseline for the maximum reduction from baseline.
Maximum Percent Increase	Defined as the percent change that is associated with the maximum most extreme change.
Duration on Study (in days)	End of study date - informed consent date +1.
Duration of Time from Initial Diagnosis to Informed Consent (in months)	(Date of Informed Consent - Date of Initial Diagnosis +1) / 30.4375.

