#### 6.2.2.1 Best Overall Response, Objective Response Rate and Durable Response Rate

##### **Best Overall Response**

Separately for injected tumors and overall (per RECIST v1.1), a participant's best overall response (BOR) is determined by the highest qualitative value assessed during the study for the following hierarchy of objective response results: CR > PR > SD > PD > NE. In order for a valid value of SD to be assigned, there must be evidence of stable disease for at least 6 weeks. If the minimum time for SD has not been met on the first assessment, the assignment of BOR will depend on subsequent response assessments. Participants which do not have follow up data after a first assessment of SD prior to the minimum time requirement will be considered as not evaluable (NE). BOR will be based on assessments collected after the first intratumoral injection until disease progression; assessments collected after the start of new anticancer treatment will not be considered. Confirmation of response will not be required for BOR. Participants who do not have any post-baseline results for response will be considered as not evaluable (NE).

Separately for injected tumors and overall (per RECIST v1.1), BOR will be summarized using the efficacy evaluable population.

Waterfall plots of BOR results for each criterion will be presented graphically using maximum percent reduction. Swimmer plots identifying participant response patterns over time will also be separately provided.

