### **Durable Response Rate**

Separately for injected tumors and overall (per RECIST v1.1), the durable response rate will be determined via persistence of CR or PR for at least 28 days, with the corresponding response duration calculation, in days, as (the earliest date of PD or death for any cause - the date of first documentation of CR or PR + 1). Participants who do not have at least 28 days of data following BOR of CR or PR will be considered to not have had durable response. Participants who discontinue prior to being evaluated for post-baseline tumor assessments will be considered as non-responders.

Separately for injected tumors and overall (per RECIST v1.1), the durable response rate will be presented; corresponding two-sided 95% Clopper-Pearson exact CIs will also be provided.

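### Partial response of injected tumors is measured from the smallest diameter, not from baseline, so gradual shrinkage over repeat cycles can go uncounted and injected-tumor ORR can be understated

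*SAP*

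**What the plan says.** The two documents give the same rule. Protocol section 9.3.4 has "Partial Response (PR): At least a 30% decrease in the longest diameter (LD) of the injected tumor(s), taking as reference the smallest LD", and the SAP repeats it in section 6.2.2 under Injected Tumor Response Criteria Details: "At least a 30% decrease in the longest diameter (LD) of the injected tumor(s), taking as reference the smallest LD".

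The progression line in the same list shows what the smallest LD means: "taking as reference the smallest LD recorded on study (this includes the baseline LD if that is the smallest on study". It is a running on-study minimum that equals baseline only while nothing smaller has been recorded. Stable disease (SD) uses the same reference. Complete response (CR) is disappearance of the tumor.

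SAP section 6.2.2 leaves no alternative reading for these lesions: "Injected tumors will not be assessed per RECIST v1.1 but solely per the criteria" of protocol section 9.3.4. It also singles out ORR for injected tumors as the efficacy endpoint of main interest, while keeping all efficacy secondary to safety. The investigator grades the response and enters it in the eCRF.

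The SAP does use baseline for its displays. Section 5.2 says that for tumor measurements "the maximum percent reduction will be the percent change from baseline for the maximum reduction from baseline", and section 6.2.2.1 adds "Waterfall plots of BOR results for each criterion will be presented graphically using maximum percent reduction".

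Protocol section 4.2 allows for several injected lesions: "All measurable tumors that are accessible for intratumoral injection will be identified and treated for each enrolled subject". The response criteria do not say whether LD then means the sum of diameters or each lesion separately.

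**The concern.** A running minimum is a sensible reference for detecting regrowth. As a reference for response it moves the target down at every visit, so the 30% fall has to occur in one step between the prior minimum and the current assessment. A tumor that shrinks steadily, by less than 30% each time, stays in SD however small it becomes.

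This pattern matters here because the trial tests repeat cycles. Protocol section 2.3 motivates repeat dosing by the short-lived responses to a single cycle, and section 12.1 justifies the 40% alternative for five cycles of therapy. Cumulative shrinkage is a plausible form of benefit, and it is what the rule fails to count.

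The stakes are the response label, injected-tumor ORR, and the measures that start from the first response: time to response, duration of response and durable response. If some sites use baseline from habit and others follow the text, grading will also differ between sites.

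**Working it through.** **1. The plan's own figures.** Protocol section 12.1 and SAP section 3.3 give n = 10, a cut-off of 3 responses, a null ORR of 10% and an alternative of 40%, with an exact one-sided binomial test.
- P(X ≥ 3 | 0.10) = 0.0702, which matches the stated 7%.
- P(X ≥ 3 | 0.40) = 0.8327, which matches the stated 83%.
- A cut-off of 2 would give an alpha of 0.264, so 3 is the right cut-off for a 10% target.

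**2. Direction of the error.** Let B be the baseline LD and M the smallest LD before the current assessment, baseline included. If the current value were included in M, PR could never occur, so this is the only workable reading.
- Written rule: PR if LD ≤ 0.7 × M.
- Baseline rule: PR if LD ≤ 0.7 × B.
- Since M ≤ B, any LD that meets the written rule also meets the baseline rule, but not the reverse. A check on 200,000 random four-assessment sequences found no exception.
- At the first post-baseline assessment M = B and the two rules agree. CR, and any single fall of 30% or more from the prior minimum, count under both.

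**3. A worked path (illustrative diameters).**

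| LD (mm) | vs baseline 50 | vs prior minimum | Baseline rule | Written rule |
|---|---|---|---|---|
| 40 | −20% | −20% | not PR | not PR |
| 32 | −36% | −20% | PR | not PR |
| 26 | −48% | −18.8% | PR | not PR |

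Best overall response is SD as written. The waterfall plot would show a bar of −48% for that participant.

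**4. How much shrinkage can be hidden.** With each fall just under 30%, the total over k assessments approaches 1 − 0.7^k: 51.0% for k = 2, 65.7% for k = 3 and 76.0% for k = 4. Imaging is planned at Day 14 of cycles 1, 3 and last (and cycle 2 if there is progression after the first), plus Day 56 of the last cycle for CR, PR or SD. Five cycles therefore give three or four scans without the cycle 2 scan.

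**5. Delay.** Assume exact 28-day cycles. Day 14 of cycles 1, 3 and 5 falls on Days 14, 70 and 126, and Day 56 of cycle 5 on Day 168. Take LDs of 100 at baseline, then 85, 69, 50 and 34 mm.
- Against baseline: −15%, −31%, −50%, −66%, so PR from Day 70.
- Against the prior minimum: −15%, −18.8%, −27.5%, −32%, so first PR at Day 168.

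Day 168 is the last planned scan. SAP section 6.2.2.1 counts "Participants who do not have at least 28 days of data following BOR of CR or PR" as not durable, so durability could not be shown. From Day 70 there would be 168 − 70 + 1 = 99 days.

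**6. Effect at n = 10.** One missed responder is 10 percentage points. Clopper-Pearson 95% limits are 6.7% to 65.2% for 3/10 and 2.5% to 55.6% for 2/10.

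**7. Illustration of the decision rule.** This assumes that the 3-of-10 rule applies to injected tumors, that the true baseline-referenced ORR is 40%, and that a share m of responders is missed. The documents give no value for m. Counted ORR is 0.40 × (1 − m).

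| m (assumed) | Counted ORR | P(≥ 3 of 10) |
|---|---|---|
| 0 | 40% | 83% |
| 10% | 36% | 76% |
| 25% | 30% | 62% |
| 50% | 20% | 32% |

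**The case against.** **RECIST wording in the protocol.** Sections 9.3.4, 10.3.3, 10.3.5 and 12.6 all tie response to RECIST 1.1, so investigators have had mixed instructions and some may grade from baseline. That stands as a reason why recorded labels may not follow the written rule. It does not repair the rule: section 9.3.4 then states its own PR reference, and the SAP says these criteria alone apply to injected tumors.

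**A disclosed difference.** The SAP says openly that endpoints differ between injected tumors and overall because the response definitions differ. Disclosure does not explain why response should be measured from a moving minimum while the plot of the same response is measured from baseline.

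**The Day 168 scan may not count.** SAP section 6.2.2.2 excludes assessments after the end of treatment from progression-free survival, and section 6.2.2.1 refers both to the whole study (best overall response) and to the treatment cycles (ORR). If the scan is excluded, the delay example becomes no PR at all, the available follow-up from Day 70 is 126 − 70 + 1 = 57 days, and the four-assessment limit of 76.0% does not apply. Those figures are conditional, but the understatement gets larger, not smaller.

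**Caliper readings.** Calipers are scheduled more often than scans, and the text does not say whether they set the minimum. The 65.7% and 76.0% limits therefore apply to grading by scans only.

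**Size and importance.** The miss rates are assumed. Phase 1 reported 66.7% response in the higher-dose cohorts after one cycle, and the two rules agree at the first scan, so the true loss may be small. The endpoint is secondary, the bias is conservative, and overall RECIST ORR and separate target-lesion response are also recorded. All of this is fair and limits the harm. It does not make the label right for the endpoint that the SAP puts first among its efficacy measures.

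**Conclusion.** The concern holds. As written in both documents, PR of injected tumors is judged against the smallest prior LD, nothing restores baseline, and a tumor 48% below baseline can be graded SD. Injected-tumor ORR is therefore equal to or lower than the baseline-referenced ORR, never higher. First-response dates can be late or missing, which carries into time to response, duration of response and durable response.

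The direction follows from the rule and needs only the reading of the smallest LD as the minimum before the current assessment. The size does not follow from the documents: it depends on how many participants shrink gradually and on whether sites apply the text literally. The fall from 83% to between 76% and 32% in the chance of meeting the 3-of-10 rule is an illustration over an assumed range. The primary safety analysis is unaffected, and the shrinkage stays visible in the baseline-referenced plots. Because a literal application gives a wrong response label on the main efficacy endpoint, this must be corrected.

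**What to change.** In protocol section 9.3.4 and SAP section 6.2.2:
- Define PR as a decrease of at least 30% in LD from the **baseline** LD. With several injected tumors, state that the sum of their LDs is used.
- Keep the smallest on-study LD as the reference for progression only.
- Define SD as neither PR against baseline nor progression against the smallest LD.
- Check or re-derive the investigator-entered injected-tumor responses from the recorded diameters where these exist.
- In SAP section 3.3 and protocol section 12.1, state whether the 3-of-10 rule uses injected-tumor or overall ORR.

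The cost is a text correction in both documents and some reprogramming, best done before database lock. No extra patients or scans are needed. Progression grading is unchanged, and CR, PR and SD all lead to the same Day 56 scan, so moving a participant from SD to PR adds no imaging. Re-derivation depends on diameters having been recorded. The CRF is not among the documents and caliper measurement is done only where possible, so some responses may need a query to the investigator.
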